7.6 Patient Reported Outcomes Analysis Set

The Efficacy Analysis Set will be used to carry out analyses for patient reported outcomes.

7.7 Interim Analysis Set

The Interim Analysis Set will include all subjects at the time when 100 subjects have completed 52 weeks of treatment with investigational product. The purpose of this interim analysis is to evaluate the long-term efficacy and safety of AMG 334 in subjects with episodic migraine after the 24-week DBTP.

7.8 Subgroup Analyses

The primary and secondary efficacy will be analyzed in the subgroups defined by the stratification factor, BMI (< median vs \geq median), baseline monthly migraine days (< 8 vs \geq 8) and treatment failure of prior migraine prophylactic medications.

8. Interim Analysis and Early Stopping Guidelines

An independent Data Monitoring Committee (DMC) will review and make recommendations regarding the safety of the study participants throughout the DBTP of the study, and until treatment assignment information is available to the study team for the primary analysis. The DMC will be composed of external advisors, including at least 2 clinicians and a biostatistician. Summaries of data at the treatment group level will be prepared and presented by an independent biostatistician at the DMC meeting.

Additionally the DMC will review pharmacokinetic data and compare the results against pre-defined criteria for observed and predicted data to potentially recommend discontinuation of enrollment into one or more of the AMG 334 treatment groups, in which case randomization of the remaining subjects would continue for the remaining treatment groups.

During the OLTP of the study, an interim analysis is planned after at least 100 subjects randomized to 70 mg of AMG 334 have completed 52 weeks of treatment with investigational product. The purpose of this interim analysis is to evaluate the long-term efficacy and safety of AMG 334 in subjects with episodic migraine after the 24-week DBTP.

9. Data Screening and Acceptance

9.1 General Principles

The objective of the data screening is to assess the quantity, quality and statistical characteristics of the data relative to the requirements of the planned analyses.

9.2 Data Handling and Electronic Transfer of Data

The Amgen Global Study Operations-Data Management (GSO-DM) department will provide all data to be used in the planned analyses. This study will use the RAVE database. The database will be subjected to edit check outlined in the Data Management Plan (DMP). eDiary data, PK, antibody, biomarkers, and ECG data are outside of RAVE database. All the datasets to be used for planned analyses will be received from GSO-DM department. Additional details will be provided in the DMP and Data Transfer Plan (DTP).

9.3 Handling of Missing and Incomplete Data

Subjects may miss specific data points for a variety of causes. In general, data could be missing due to a subject's early withdrawal from study, a missed visit, or inability to evaluate an endpoint at a particular point in time. For this study, most of the efficacy endpoint will be collected via eDiary and subjects could miss entering several days of data in each monthly interval. The general procedures outlined below describe what will be performed when a data point is missing.

Missing eDiary data in the calculation of monthly measurements about subjects' migraine and non-migraine headaches will be handled using the following method.

1. For monthly intervals with ≥ 14 days of eDiary days (including retrospective eDiary days) in each interval:
 - a) Monthly frequency measurements (including migraine days, headache days, migraine attacks, cumulative hours of migraine headaches, acute medication use, bed days due to migraine and missed work/school days due to migraine) will be prorated to 28-day equivalents. Prorated result does not need to be rounded.
 - b) Monthly average severity of migraine pain, migraine related symptoms and monthly average scale of migraine interference with daily activity will calculated as the average of observed scores
2. For monthly intervals with < 14 days of eDiary use (including retrospective eDiary days), all monthly measurement will be set as missing and will be handled as described in [Section 9.3.3](#)

Missing eDiary data in the calculation of cumulative average monthly measurements about subjects' migraine and non-migraine headaches is treated as if subjects do not have headache or medication use to report.

Missing PROs (HIT-6) scheduled to be collected at office visit at certain assessment will not be imputed.

Missing safety endpoints will not be imputed. Missing day portion of AE start time will be imputed based on [Section 9.3.1](#).

Missing pharmacogenetic and antibody data will not be imputed.

Handling of missing or incomplete data for exposure-response analysis will be described in the E-R SSAP or associated documents to support population PK/PD dataset generation and E-R analysis.

9.3.1 Missing and Incomplete Dates

Missing or incomplete dates will be listed as it is in any listings.

Incomplete start date of an adverse event or concomitant medication taken will be handled by following rule:

	Missing	Imputation	Exception
Start date (AE, concomitant medication)	Day	01	Default to Study Day 1 if an adverse event starts the same year and month as Study Day 1 and the flag indicates that the adverse event started on or after the first dose on the Adverse Events eCRF
	Day/Month	01JAN	Default to Study Day 1 if an event started the same year as Study Day 1 and the flag indicates that the adverse event started on or after the first dose on the Adverse Events eCRF
	Day/Month/Year	No imputation	

9.3.2 Missing Baseline Evaluation

Baseline values are defined in [Section 6.3](#) “Baseline Assessment of the Study”. Missing baseline evaluations will not be imputed.

All subjects included in the efficacy analysis set will have baseline monthly rate or monthly average of migraine and non-migraine headaches related measurements after applying proration rule defined in [Section 9.3](#) since only subject with $\geq 80\%$ compliance of eDiary use during baseline will be eligible for randomization.

9.3.3 Missing Post-baseline Evaluation in Double-Blind Treatment Phase

Primary analysis of efficacy endpoints during the 24-week randomized DBTP will be conducted using the repeated measures linear mixed effects model on observed data without imputation.

For the descriptive summary of mean monthly value calculated using the monthly value from each of the last three months (months 4, 5, and 6) of the DBTP, if a subject has at least one month's value in months 4, 5, and 6, then the subject contributes to the summary statistics.

In the sensitivity analysis on primary and secondary efficacy endpoints during the 24-week DBTP, missing continuous efficacy endpoints will be handled using last observation carried forward (LOCF) method, inverse probability weighting (IPW) generalized estimation equations (GEE) method, and multiple imputation (MI) with assumption of missing at random (MAR), respectively.

In LOCF method, post-baseline missing continuous efficacy endpoints during DBTP will be imputed using the last observed value including baseline value. For example, if subject has all of the post-baseline values as missing, then all of the post-baseline values will be imputed using the observed baseline value.

In non-responder imputation (NRI) method, post-baseline missing dichotomous secondary efficacy endpoint (responder (Yes/No) based on $\geq 50\%$ reduction from baseline in monthly migraine days) during DBTP will be imputed as non-responder at each corresponding time point.

IPW GEE method will be used to handle monotone missing data during DBTP. Intermittent missing data during DBTP will be handled by LOCF or NRI method before applying IPW GEE method.

If the proportion of missing data in primary endpoint is high (eg, $> 20\%$ for primary analysis at week 24), further analysis will be performed to

- examine the frequency and reason of missing data
- determine if there are any patterns in the missing data
- distinguish true missing values from other unknown values (eg, due to measurement or sample processing error)

9.4 Detection of Bias

This study has been designed to minimize potential bias by allocating treatment groups randomly, assessing endpoints and handling withdrawals without knowledge of the treatment. Other factors that may bias the results of the study include:

- important protocol deviations likely to impact the analysis and interpretation of the efficacy endpoints
- inadvertent breaking of the blind before formal unblinding
- investigational product dosing non-compliance
- the timing of and reasons for early withdrawal from treatment and from study

The incidence of these factors may be assessed. Important protocol deviations will be listed and/or tabulated in the clinical study report (CSR). If necessary, the incidence of other factors will be tabulated.

Any breaking of the blind for individual subjects prior to formal unblinding of the study will be documented in the CSR.

The timing of and reasons for early withdrawal from treatment and from study will be tabulated and/or listed.

9.5 Outliers

Histograms will be examined to identify outliers in any of the continuous variables used in the analyses. Unexpected and/or unexplained values in categorical data will be identified by utilizing frequency tables.

Outliers due to data entry errors will be corrected by the study team before final database lock. The validity of any questionable values or outliers will be confirmed.

Outliers or any questionable values with confirmed validity will be included in the analyses. However, ad-hoc sensitivity analyses may be conducted to evaluate the influence of extreme values in the data.

9.6 Distributional Characteristics

Continuous endpoints of change from baseline value will be analyzed under normality assumption. If they deviate appreciably from normality, appropriate transformations or the non-parametric alternatives such as Quade test (Quade D, 1966) may additionally be considered. For repeated measure analysis, GEE model which is less sensitive to normality violation may be used in addition to the mixed effect model.

9.7 Validation of Statistical Analyses

Programs will be developed and maintained, and output will be verified in accordance with current risk-based quality control procedures.

Tables, figures and listings will be produced with validated standard macro programs where standard macros can produce the specified outputs.

The production environment for statistical analyses consists of Amgen-supported versions of statistical analysis software, for example the SAS System and S-plus.

For the exposure-response analysis, refer to the E-R SSAP for the software used.

10. Statistical Methods of Analysis

10.1 General Principles

The primary objective of this study is to evaluate the effect of AMG 334 compared to placebo on the change from baseline in mean monthly migraine days, in subjects with episodic migraine.

The primary analysis will be performed when the last randomized subject completes the week 24 assessment or is discontinued from the study. The final analysis for the study including DBTP, OLTP and safety follow-up phase will be performed at the end of the study.

Subjects will be analyzed based on their randomized treatment group assignment.

Summary descriptive statistics by each treatment group will be tabulated at each visit. For continuous endpoints, the descriptive statistics include: number of observations, mean, median, standard deviation, first and third quartiles, minimum and maximum. For categorical and ordinal endpoints, frequency and percentage will be given.

Change from baseline for efficacy endpoints will be summarized using both the study baseline and the pre-OLTP baseline for efficacy endpoint, respectively.

Primary analyses for efficacy endpoints are based on a linear mixed effects model including appropriate terms and covariates in the model (See [Section 4.2](#)). Nominal p-values will be provided for the comparisons between each AMG 334 treatment group vs. the placebo group for efficacy endpoints. To maintain a family-wise type I error at 0.05, the pair-wise comparison will be tested in a sequential testing procedure in the order of AMG 334 140 mg vs. placebo, 70 mg vs. placebo and 28 mg vs. placebo. The lower dose group will be tested only when the higher dose group is considered statistically significant. For continuous efficacy endpoints, the adjusted mean change from baseline

for each treatment group, and the adjusted treatment difference compared to placebo, associated 95% confidence intervals, and p-values for pairwise comparison will be reported. For dichotomous efficacy endpoints, adjusted odds ratios compared to placebo, associated 95% confidence intervals, and p-values will be reported. Randomized stratum (stratification group) will be included in the statistical models for the efficacy endpoints. However, the actual data collected will be used for the analysis of baseline characteristics and subgroup analyses.

10.2 Subject Accountability

For the primary analysis at week 24, the disposition of all enrolled subjects will be tabulated by the randomized treatment group. The summary will include the number of subjects who are randomized, the number and percent of subjects who receive the double-blind IP, who complete double-blind IP, discontinue double-blind IP and reasons for discontinuing, who complete the 24-week DBTP, and who withdraw prematurely from the study before completion of the 24-week DBTP and their reasons for withdrawal.

For the final analysis, disposition of the OLTP and safety follow-up phases will be added, which include the number and percent of subjects who enter the OLTP, who receive AMG 334, who complete AMG 334, discontinue AMG 334 and reasons for discontinuing, who complete the OLTP, who complete the study, and who withdraw prematurely from the study and their reasons for withdrawal.

A footnote on the subject disposition tables will include the number of subjects screened, date first subject enrolled, date last subject enrolled, the date of study primary completion, the date of study completion (eg, last subject completed the safety follow-up visit or drop out from the study) and corresponding data cutoff date.

10.3 Important Protocol Deviations

Important Protocol Deviations (IPDs) categories are defined by the study team before the first subject's visit and updated during the IPD reviews throughout the study prior to database lock. These definitions of IPD categories, sub-category codes and descriptions will be used during the course of the study. Eligibility deviations are defined in the protocol. IPDs will be summarized by randomized treatment group and listed for DBTP and OLTP, respectively.

10.4 Demographic and Baseline Characteristics

Subject demographic and baseline characteristics will be summarized using descriptive statistics by randomized treatment group and overall study population using FAS. If

multiple races have been reported for a subject, the subject will be categorized as multiple race.

The following demographic and baseline characteristics will be summarized:

- Age
- Sex
- Ethnicity
- Race
- Height (cm)
- Weight (kg)
- Body Mass Index (BMI, kg/m²)
- Targeted neurological disease diagnosis at baseline
- Disease duration of migraine with or without aura
- Age at onset of migraine
- Migraine specific-medications subjects used during baseline phase:
 - a. Triptan-based
 - b. Ergotamine-based
- Monthly acute migraine-specific medication use in days during baseline phase
- Prior/current treatment with migraine prophylactic medication (current migraine prophylactic medication treatment vs prior migraine prophylactic medication treatment only vs no prior or current migraine prophylactic medication treatment)
- Monthly migraine days during baseline phase
- Monthly migraine attacks during baseline phase
- Monthly headache days during baseline phase
- Prior prophylactic treatment failure (Yes vs. No)

10.5 Efficacy Analyses

Primary analysis of efficacy endpoints will utilize the efficacy analysis set. Subjects will be analyzed according to their randomized treatment group regardless of the actual

treatment received during the study. Per protocol analysis of the primary and secondary endpoints will utilize the Per Protocol Set.

For primary analysis at week 24, the continuous change from baseline efficacy endpoints as specified in [Section 9.3](#) will be analyzed using linear mixed effect models adjusted by stratification factor and baseline value on observed data as the primary analysis method. The dichotomous efficacy endpoints will be analyzed using the stratified Cochran-Mantel-Haenszel (CMH) test after the missing data are imputed as non-response.

Detailed primary analysis methods, sensitivity analyses, and covariates included in the models are summarized in the table below.

Table 1. Summary of Efficacy Endpoints and Analysis Methods

Endpoint	Primary Summary and Analysis Method	Sensitivity Analysis
Primary Endpoint		
Change from baseline in monthly migraine days (Note: Results from time points during DB treatment phase will also be generated in the same model.)	
Summary statistics by visit using observed data, and using mean monthly migraine days at month 4,5,6Least squares mean at each timepoint from a linear mixed effect model adjusted by stratification variable and baseline value using observed dataTest pairwise treatment difference between active and placebo for the primary endpoint – change from baseline in mean monthly migraine days, using a contrast from the model in #2.	
LOCF: Summary statistics by visit and analyze using an ANCOVA model for the mean monthly migraine days.Per-Protocol subset: Same as primary summary and analysis method.IPW GEE model for change from baseline in monthly migraine daysMI with assumption of MAR
Secondary Endpoints		
Response defined as at least a 50% reduction from baseline in mean monthly migraine days (Note: Results	
Summary statistics by visit using observed data, and responder rate calculated using mean monthly migraine days at month 4,5,6A stratified Cochran-Mantel-Haenszel (CMH)	
Without imputation, adjusted odds ratios from a generalized linear mixed model adjusted by stratification variable and baseline migraine days by visit using observed data, and using responder rate calculated using mean monthly migraine days at month 4,5,6NRI: Summary statistics by visit and

Endpoint	Primary Summary and Analysis Method	Sensitivity Analysis
from time points during DB treatment phase will also be generated in the same model.)	test will be used after the missing data are imputed as non-response	analyze using a logistic regression model, and using responder rate calculated using mean monthly migraine days at month 4,5,6 3. Per-Protocol subset: Same as primary summary and analysis method.

Endpoint	Primary Summary and Analysis Method	Sensitivity Analysis
Change from baseline in monthly acute migraine-specific medication treatment days (Note: Results from time points during DB treatment phase will also be generated in the same model.)	
 1. Summary statistics by visit using observed data and using mean monthly acute migraine-specific medication treatment days 2. Least squares mean at each timepoint from a linear mixed effect model adjusted by stratification variable and baseline value using observed data 3. Test pairwise treatment difference between active and placebo for the endpoint of change from baseline in mean monthly acute migraine-specific medication treatment days, using a contrast from the model in #2. 	
 1. LOCF: Summary statistics by visit and analyze using an ANCOVA model. 2. Per-Protocol subset: Same as primary summary and analysis method. 3. IPW GEE model for change from baseline in monthly acute migraine-specific medication treatment days 4. MI with assumption of MAR
Exploratory Endpoints		
Change from baseline in monthly headache (migraine and non-migraine headache) days at assessment time points ^a	
 1. Summary statistics by visit using observed data and mean monthly headache 2. Least squares mean at each timepoint from a linear mixed effect model adjusted by stratification variable and baseline value using observed data 3. Test pairwise treatment difference between active and placebo for the corresponding endpoint of change from baseline in mean monthly values, using a contrast from the model in #2. 	
Response defined as at least a 75% reduction from baseline in mean monthly	
 1. Summary statistics by visit using observed data and responder rate calculated using mean monthly migraine days at month 4,5,6 	

Endpoint	Primary Summary and Analysis Method	Sensitivity Analysis
migraine days (Note: Results from time points during DB treatment phase will also be generated in the same model.)^b	2. Adjusted odds ratios from a generalized linear mixed model adjusted by stratification variable and baseline migraine days by visit using observed data, and using responder rate calculated using mean monthly migraine days at month 4,5,6	

a: The same analyses methods will be applied to the endpoints:

Change from baseline in mean headache impact scores as measured by HIT-6 (HIT-6 total score),
Change from baseline in monthly migraine attack,
Change from baseline in monthly cumulative migraine hours,
Change from baseline in monthly average severity of migraine pain,
Change from baseline in monthly migraine days with severe pain,
Change from baseline in monthly cumulative hours of migraine with severe pain,
Change from baseline in monthly acute medication use in days,
Change from baseline in monthly average migraine symptoms interference scale,
Change from baseline in monthly bed days due to migraine related symptoms,
Change from baseline in monthly missed work/school days due to migraine related symptoms.

b: The same analyses methods will be applied to the endpoints:

Response defined as at least a 100% reduction from baseline in mean monthly migraine days.

10.5.1 Analyses of Primary and Secondary Efficacy Endpoints

For the primary analyses at the end of DBTP, the continuous primary and secondary endpoints will be tested using a linear mixed model based on observed monthly data from 24-week DBTP with appropriate contrasts provided in [Appendix B](#) for pairwise comparisons for the corresponding efficacy endpoints: change from baseline in mean monthly values.

The model will include treatment, visit, treatment by visit interaction, stratification variable and baseline value as covariates. If applicable, the first-order autoregressive covariance structure is assumed. Least squares means (LSMs) for each treatment group, standard errors, associated 95% confidence intervals, difference of LSMs compared to placebo group, associated 95% confidence intervals and nominal two-sided p-values will be tabulated by visit and treatment, as well as for the mean monthly values over the last 3 months in DBTP.

For binary endpoints, adjusted odds ratios compared to placebo group, associated 95% confidence intervals and nominal two-sided p-values will be tabulated by visit and treatment.

Sensitivity analysis described below will be performed for the primary and secondary endpoints:

1. Summary statistics and ANCOVA model for continuous endpoints (logistic regression model for binary endpoints) by visit using imputed data by LOCF (NRI for binary endpoint). Factor of treatment, baseline covariate and stratification variable will be included in the model.
2. Inverse probability weighted generalized estimation equation (IPW GEE) model on the primary and secondary endpoints.
3. MI with assumption of MAR
4. Primary summary and analysis method based on per protocol analysis set.
5. Primary summary and analysis by the subgroup of
 - Prior/current treatment with migraine prophylactic medication (current migraine prophylactic medication treatment vs prior migraine prophylactic medication treatment only vs no prior or current migraine prophylactic medication treatment)
 - BMI (< median vs. \geq median)
 - Baseline monthly migraine days (< 8 vs \geq 8)
 - Treatment failure of prior migraine prophylactic medications
6. Primary summary and analysis method with interaction: If the inclusion criterion at the 0.15 level is met, the interaction of treatment group by stratification variable will be included in the model as sensitivity analysis for the primary analysis method.

The purpose of the subgroup analyses is to explore if the treatment effect varies across subgroups of interest. Subgroup analyses are performed for primary and secondary efficacy endpoints using the same method as Primary Summary and Analysis Method but performed within each described subgroup.

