3.1.1 Double-blind Treatment Phase

Approximately 459 eligible subjects will be randomized in a 2:1:2:2 ratio to 1 of 4 treatment groups: placebo, AMG 334 28 mg, AMG 334 70 mg, or AMG 334 140 mg, with approximately 131 subjects assigned to placebo, approximately 66 subjects assigned to AMG 334 28 mg, approximately 131 subjects assigned to AMG 334 70 mg, and approximately 131 subjects assigned to AMG 334 140 mg. The randomization will be stratified by prior/current treatment with migraine prophylactic medication (current migraine prophylactic medication treatment vs prior migraine prophylactic medication treatment only vs no prior or current migraine prophylactic medication treatment). There will be a limit on the percentage of subjects on current migraine prophylactic medication treatment.

Amgen investigational product (ie, AMG 334 28 mg, AMG 334 70 mg, AMG 334 140 mg, or placebo) will be dosed monthly (QM) by subcutaneous (SC) injections. Double-blind AMG 334 140 mg, AMG 334 70 mg, AMG 334 28 mg, or placebo will be administered during the 24-week DBTP (ie, at day 1 and weeks 4, 8, 12, 16, and 20).

Migraine and non-migraine headache outcomes and other efficacy measures will be assessed based on eDiary data. Subjects will also have in-clinic study visits at Day 1 and monthly visits thereafter.

Subjects who permanently discontinue investigational product during the DBTP are to continue to return for all other study procedures until the end of the DBTP and study procedures for the safety follow-up visit 16 weeks after the last dose of investigational product.

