3.2 Sample Size

The primary endpoint is the change from baseline in mean monthly migraine days over the last three months (months 4, 5, and 6) of the DBTP. Using the treatment effect compared to placebo of -1.12 and -1.30 for the AMG 334 70 mg and 140 mg dose groups, respectively and a common standard deviation of 2.8 based on a placebo-controlled dose-finding study of JNS019 (topiramate) in migraine patients (www.clinicaltrials.gov), the planned sample size of 131 subjects in the placebo, 70 mg and 140 mg dose groups will provide 90% and 96% power for a two-sided test with significance level of 0.05 to show the difference of AMG 334 70 mg and 140 mg compared to placebo, respectively. The proposed number of subjects in the 28 mg (n=66) dose group with the placebo (n=131), the 70 mg (n=131) and the 140 mg (n=131) dose groups is sufficient to demonstrate a dose-response using Multiple Comparison Procedure – Modelling (MCP-Mod) analysis with minimum power of 95% and provide estimates of response in a Japanese population, using an assumed treatment effect of -0.55 for the AMG 334 28 mg dose group.

Power calculations are derived through nQuery 7.0.

4. Study Endpoints and Covariates

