Assume that there are n_i repeated measurements of the response on the i^{th} subject and that each Y_{ij} is observed at time t_{ij} , with associated covariates X_{ij} , which can be time-stationary or time-varying. A marginal model for longitudinal data has the following three-part specification:

1. The conditional expectation or mean of each response, $E(Y_{ij}|X_{ij}) = \mu_{ij}$, is assumed to depend on the covariates through a known link function

$$g(\mu_{ij}) = \eta_{ij} = X_{ij}'\beta.$$

2. The conditional variance of Y_{ij} , given the covariates, is assumed to depend on the mean according to

$$\text{Var}(Y_{ij}) = \phi v(\mu_{ij}),$$

where $v(\mu_{ij})$ is a known “variance function” (ie a known function of the mean, μ_{ij}) and ϕ is a scale parameter that may be known or may need to be estimated.

3. The conditional within-subject association among the vector of repeated responses, given the covariates, is assumed to be a function of an additional set of association parameters, α (and also depends upon the means, μ_{ij}). For example, the components of α might represent the pairwise correlations or log odds ratios among the repeated responses.

The avoidance of distributional assumptions leads to a method of estimation known as *generalized estimating equations (GEE)*. The GEE estimator of β for marginal models can be thought of as arising from minimizing the following objective function:

$$\sum_{i=1}^N \{y_i - \mu_i(\beta)\}' V_i^{-1} \{y_i - \mu_i(\beta)\},$$

With respect to , where V_i is treated as known (by ignoring its dependence on β through μ_i) and μ_i is the vector of mean responses, with elements

$$\mu_{ij} = \mu_{ij}(\beta) = g^{-1}(X_{ij}'\beta)$$

Using calculus, it can be shown that if a minimum of the above function exists, it must solve the following *generalized estimating equations*:

$$\sum_{i=1}^N D' V_i^{-1} \{y_i - \mu_i\} = 0,$$

where $D_i = \partial \mu_i / \partial \beta$ is the derivative matrix and V_i is the so called working covariance matrix, which approximates the true underlying covariance matrix for Y_i , that is, $V_i \cong \text{Cov}(Y_i)$, recognizing that $V_i \neq \text{Cov}(Y_i)$ unless the models for the variance and the within-subject associations are correct. Parameter estimates from the GEE are precise or efficient as the MLE and are consistent even when the variance structure is misspecified, under mild regularity conditions.

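### The primary mixed model has only an undefined, conditional AR(1) covariance in the readable SAP, so the size of the months 4–6 test depends on an unstated choice

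*SAP*

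**What the plan says.** SAP 10.5.1 tests the primary endpoint by a contrast over months 4, 5 and 6, taken from a linear mixed model fitted to the six monthly values. The fixed effects are treatment, visit, their interaction, stratum and baseline. On covariance it says only "If applicable, the first-order autoregressive covariance structure is assumed". Protocol 10.5.2 specifies a repeated-measures mixed model and names no structure.

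The secondary endpoint of migraine-specific medication days uses the same model. Subgroups are analysed "using the same method as Primary Summary and Analysis Method but performed within each described subgroup".

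SAP Appendix A1 describes linear mixed models as having normal random effects, and A2 contrasts them with marginal models on that ground. A1 also allows models with no random effects beyond the residual structure. The code in Appendix B is redacted. It may hold a random intercept, a robust standard error, a degrees-of-freedom method or a fallback, and none of these is treated here as missing.

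On multiplicity, SAP 10.1 states: "To maintain a family-wise type I error at 0.05, the pair-wise comparison will be tested in a sequential testing procedure". The 140 mg comparison comes first.

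**The concern.** AR(1) forces equal variance at all six visits and a correlation that decays geometrically with the gap between visits. If each subject has a stable underlying migraine frequency, months far apart stay correlated and the decay is wrong. If the spread of the changes grows or shrinks over time, the equal-variance assumption is wrong. Either way, the model-based standard error of the months 4–6 contrast can miss the true one.

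That standard error drives the primary p-values and 95% intervals for all three doses, and those for medication days. The 140 mg test opens the fixed sequence. If no dose works, the family-wise error therefore equals the size of that one test. The words *if applicable* leave open, in the readable text, a choice that changes this standard error.

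**Working it through.** **Inputs from the SAP.** Section 3.2: 131 subjects per arm (placebo, 70 mg, 140 mg), effects −1.12 and −1.30 days, "a common standard deviation of 2.8 based on a placebo-controlled dose-finding study", two-sided 0.05. Section 10.5.1: six monthly values and a months 4–6 contrast. The within-subject covariance is not given, so it is assumed and varied.

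**Step 1: the plan's own figure.** SE = 2.8 × √(2/131) = 0.346.
- 70 mg: 1.12/0.346 = 3.24; power = Φ(3.24 − 1.96) = 89.9%.
- 140 mg: 1.30/0.346 = 3.76; power = Φ(3.76 − 1.96) = 96.4%.

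The stated 90% and 96% reproduce. They use an endpoint-level SD, so the covariance choice does not touch them.

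**Step 2: method.** Let c = (0,0,0,1,1,1)/3, S the assumed true 6×6 covariance, and V the fitted structure that minimises log|V| + tr(V⁻¹S), which is the large-sample fit. The SE ratio is r = √(c′Vc / c′Sc), and the size is 2 × (1 − Φ(1.96 r)).

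*Worked case.* The truth is exchangeable with correlation 0.5 and unit variance; the fitted AR(1) has variance 1 and correlation 0.5.
- True variance of the contrast: (3 + 6 × 0.5)/9 = 0.667.
- AR(1) variance: (3 + 4 × 0.5 + 2 × 0.25)/9 = 0.611.
- r = √(0.611/0.667) = 0.957; size = 2 × (1 − Φ(1.877)) = 6.1%.

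**Step 3: size across assumed truths (nominal 5%).** SD drift is linear over the six visits.

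| Assumed truth | AR(1) alone | Random intercept + AR(1) |
|---|---|---|
| AR(1), correlation 0.6 | 5.0% | 5.0% (contains the truth) |
| Exchangeable 0.4–0.8, constant SD | 5.5–6.1% | 5.0% |
| Subject effect (30–70% of variance) plus serial correlation 0.3–0.6, constant SD | 5.1–5.5% | 5.0% |
| Exchangeable 0.4–0.8, SD rising 10% | 6.2–6.9% | 5.7% |
| Exchangeable 0.4–0.8, SD rising 20% | 6.8–7.5% | 6.3% |
| Exchangeable 0.4–0.8, SD falling 10% | 4.7–5.3% | 4.3% |
| Exchangeable 0.4–0.8, SD falling 20% | 3.9–4.4% | 3.5% |

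**Step 4: check by simulation.** The four-arm model (459 subjects, baseline and stratum included, REML AR(1), 2,500 runs per setting) was run under exchangeable data. The mean size over the three dose comparisons, with no dropout / an assumed 10% dropout, was:
- correlation 0.35: 6.0% / 6.6%
- correlation 0.5: 6.3% / 6.4%
- correlation 0.7: 6.0% / 5.7%

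Monte Carlo error is about 0.5 points per comparison, so this agrees with Step 3. In a separate simulation with complete data and no covariates (200,000 runs), an unstructured covariance held 4.9–5.1% in every scenario, at 459, 92 and 46 subjects.

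**Step 5: effect on intervals.** The true 95% half-width is 1.96 × 0.346 = 0.68 days. With AR(1) alone and constant variance, r runs from 0.955 to 0.996, so the reported half-width is 0.65 to 0.675 days and coverage is 93.9–94.9%.

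**The case against.** The strongest objection is that AR(1) alone is not established as the plan. Both documents call this a mixed effects model, and Appendix A explains mixed models through random effects, so a random subject intercept with AR(1) residuals is a natural reading. Under it, both constant-variance scenarios lie inside the model and the size is 5.0%. The redacted code may say exactly this. The objection stands, and for that reason the sizes are conditional. It does not remove the point: A1 also permits a residual-only model, the sentence in 10.5.1 does not choose, and a random intercept still leaves 3.5–6.3% when the SD drifts by 20%.

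Second, cross-checks are planned. Under LOCF the SAP will "analyze using an ANCOVA model for the mean monthly migraine days", which uses one value per subject and so does not depend on within-subject covariance. IPW GEE and multiple imputation are also listed, and section 9.6 adds that a "GEE model which is less sensitive to normality violation may be used in addition to the mixed effect model". These would probably expose a large distortion, but none replaces the primary p-value.

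Two stronger readings are tempting. A reader might infer that the primary test is anti-conservative. The documents give no correlation or variance pattern, and with a falling SD the test can be conservative, so neither inflation nor its direction is established. A reader might also take Appendix A2 as an admission of the problem, since it says the working covariance differs from the true one "unless the models for the variance and the within-subject associations are correct". That passage concerns GEE; it goes on to say the estimates remain consistent, and it does not say that a mixed-model standard error is too small.

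**Conclusion.** The point holds as an unresolved choice with a modest, conditional effect. The readable SAP leaves the primary covariance to an undefined condition. If that means AR(1) alone with model-based standard errors, a stable subject level with constant variance raises the size by at most about 1.1 points. SD drift of up to 20% widens the range to about 3.9–7.5%. A random intercept removes the first effect but not the second.

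All true covariances are assumed, and the redacted code may already resolve the matter. No conclusion is shown to be at risk: the expected z values at the planned effects, 3.24 and 3.76, are far above 1.96. This is a cheap improvement that the sponsor should make, not a flaw that invalidates the analysis.

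**What to change.** Replace the covariance sentence in SAP 10.5.1 with:

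*An unstructured covariance across the six monthly visits will be used with Kenward-Roger degrees of freedom; if it does not converge, a heterogeneous Toeplitz structure, then AR(1) plus a random subject intercept, will be used in that order.*

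If Appendix B already specifies an equivalent, align the text of 10.5.1 with it.

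**Cost.** One sentence and a few model options, with no new data. The structure has 21 parameters (6 × 7/2) against 459 subjects.

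**Downside.** Non-convergence is possible, and intervals may be slightly wider in small subgroups. The current-prophylaxis stratum is the likely small one, since "There will be a limit on the percentage of subjects on current migraine prophylactic medication treatment", at a share not stated. Assuming 92 or 46 subjects there and complete data, the unstructured interval ranged from 0.3% narrower to 4.6% wider than under AR(1). With an assumed 15% dropout it converged in all 2,042 simulated fits, but those runs were too few to judge its error rate. The last fallback still assumes constant variance, so it should remain a last resort.
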